11.1 Primary Efficacy Endpoint Sensitivity Analysis

As a sensitivity analysis, all types of missingness will be addressed via multiple imputation, with a target of 100 multiply imputed datasets. These analyses will be created for findings obtained initially with all available data, with subsequent analysis and pooling performed to evaluate if missing data produces bias in model point estimates or otherwise influences the inferential process.

Multiple imputation will be performed via PROC MI in SAS v9.4. The variables used in the imputation model are the six pre-specified sub-groups of interest, along with any relevant measurements for a subject that will better inform the imputation process (e.g., with missing Day 8 D-dimer, one would include baseline D-dimer in the model). The missing data mechanisms theoretically conferring unbiased estimation (given appropriate covariate selection in the imputation model) using this methodology are MCAR and MAR, although “modern” methodology (MI or FIML [full information maximum likelihood]) also demonstrates superior properties to listwise deletion et al in the MNAR case. Reference Appendices in [Section 14.2](#) which contain descriptions of the Bayesian models, methods for multiple imputation, and methods for power analysis used in this study.

11.2 Primary Efficacy Endpoint Subgroup Analyses

In order to test for subgroup sensitivities, a Bayesian generalized linear mixed effects model will be constructed. This model will evaluate the influence of pre-specified subgroups of interest, D-dimer stratum, and potential site-level heterogeneity in patient outcomes.

A separate set of analyses for each rNAP2 dosing instance will be constructed, such that the effect on D-dimer of each incremental dose of rNAP2 is estimated. These analyses will therefore be equivalent in

formulation to the Primary Efficacy Analysis as specified above, with estimates of instantaneous treatment effect at Days 3, 5, and 8 for subjects receiving 1, 2 or 3 doses of rNAPc2 or receiving SoC heparin through days 1, 3, and 7, respectively.

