2.2 BACKGROUND

rNAPc2 is a novel, potent ($K_i = 10$ pM), highly selective TF inhibitor with anticoagulant, anti-inflammatory, and potential antiviral properties.

Mechanism of action

rNAPc2 inhibits the quaternary complex of TF/activated factor X (fXa) /fVIIa that catalyzes thrombin formation, by a unique mechanism requiring initial binding of rNAPc2 to zymogen or fXa before formation of the final quaternary inhibitory complex (Figure 3). The TF/fXa/fVIIa complex also activates the pro-inflammatory protease activated receptors PAR1 and PAR2;

inhibition of this signaling is the likely basis for the anti-inflammatory effects of rNAPc2 in humans.^{20,21} Cell derived TF incorporated into virus envelope substantially promotes infectivity¹⁵ and is inhibited by rNAPc2 through the same mechanism of forming an inhibitory quaternary complex which is presumably why rNAPc2 reduced viral load in Ebola-infected monkeys and Herpes simplex virus 1 (HSV1)-infected mice.^{12,16}

Clinical data with rNAPc2

Pharmacokinetics: Systemic exposure to rNAPc2 increased with increasing doses from 1.5 to 5.0 $\mu\text{g}/\text{kg}$ SC with no significant differences in T_{max} among doses. The mean $t_{1/2}$ values ranged from 47.0 to 64.1 hours following the first dose on Day 1 and from 70.8 to 78.9 hours following the third dose on Day 5 and are independent of route of administration (intravenous [IV] or SC). The prolonged $t_{1/2}$ in humans has been determined to be a result of stoichiometric binding of rNAPc2 to fX in plasma.²² SC bioavailability, estimated in the dog and cynomolgus monkey, was in excess of 95% and rNAPc2 was undetected in urine.

There have been six Phase 1 and 3 Phase 2 trials of rNAPc2 that enrolled 800 participants. A total of 704 participants have received rNAPc2 via IV (N=235) and SC (N=469) administration. In these trials, there were 174 participants who received a single dose of rNAPc2 and 530 participants who received multiple doses of rNAPc2. Early phase clinical studies with rNAPc2 are summarized (Table 1).

[figure not shown]

Figure 3. rNAPc2 mechanism of action: 1) rNAPc2 binds tightly to zymogen factor X; 2) docking of the rNAPc2-fX complex to TF/fVIIa assembled on a procoagulant phospholipid surface; and 3) presentation of the reactive loop of rNAPc2 to the active site of fVIIa, resulting in a tightly bound quaternary inhibitory complex. c2 rNAPc2; TF tissue factor; VIIa fVIIa; X factor X¹⁹

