2.2 Sample Size Determination

During Phase 2b, approximately 160 participants will be enrolled and randomized 1:1:2 to rNAPc2 dose regimen 1, rNAPc2 dose regimen 2, and heparin SoC, respectively. Assuming approximately 20% of participants may not be evaluable for any reason, 160 randomized participants will provide for approximately 130 evaluable participants. At a sample size of 160, the study will have adequate power across a range of clinically meaningful effect sizes, operationalized as proportional reductions in D-dimer (relative to heparin) from 20% to 40% in increments of 5% (see below). This sample size was selected, based on a statistical simulation using Wilcoxon rank sum and assuming a 20% missing/dropout rate, to ensure inferences for the primary endpoint analysis will be robust, given certain potential confounding factors such as missing data (random or non-random), heterogeneous application of heparin (low molecular weight and unfractionated; prophylactic and therapeutic), effects of subject-level covariates (e.g., comorbidities), and effects of site-level covariates (e.g., country).

Power, Primary Endpoint							
	Effect Size (Proportional Reduction)						
	Enrolled Subjects	Evaluable Subjects	20%	25%	30%	35%	40%
Sample Size	80	64	55.8%	67.4%	75.6%	81.0%	84.5%
	100	80	60.5%	72.7%	80.1%	84.9%	87.8%
	110	88	63.6%	76.2%	80.7%	86.6%	89.2%
	120	96	65.2%	78.0%	82.8%	86.9%	91.0%
	130	104	68.2%	79.3%	84.8%	88.7%	91.7%
	140	112	68.9%	80.7%	86.6%	89.3%	92.5%
	160	128	71.3%	83.1%	88.3%	91.3%	94.1%
	180	144	74.9%	84.5%	89.5%	92.5%	94.6%
	200	160	77.2%	86.5%	91.0%	93.8%	95.8%

*Significance via $\alpha = 0.05$
 †Simulated with 20% Missing Data
 ‡Percentages as Averages Across Other Simulation Conditions

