7.1 Primary Efficacy Endpoint

The primary efficacy endpoint of Phase 2b is proportional change in D-dimer level from baseline (Day 1 visit where randomization occurs and central laboratory samples are drawn) to Day 8, or Day of Discharge if prior to Day 8 between treatment groups. The primary analysis will involve a comparison of the pooled rNAPc2 treatment groups against the heparin treatment group.

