7.1.1 Primary Analysis of the Primary Efficacy Endpoint

Proportional change, represented by percent change, will be calculated as $100 \times (\text{D-Dimer level at Day 8 or Day of Discharge if prior to Day 8} - \text{D-Dimer level at baseline}) / \text{D-Dimer level at baseline}$ and will be based on data provided by the central laboratory, or local laboratory paired samples if the central laboratory values are not available. The pairing process will be operationalized as outlined:

For Day 1 (baseline) paired local-local or central-central laboratory values:

1. Use any lab D-dimer drawn during the current admission and up to randomization

2. Use the laboratory sample closest to randomization if there are multiple D-dimer measurements.
3. All samples obtained more than 1-hour post-initiation of study drug are ineligible.

For Day 8 or Day of Discharge paired laboratory values:

1. Use laboratory samples collected within ± 48 h of the Day 8 or Day of Discharge study visit (whichever occurs first).
2. If there are multiple laboratory samples collected within that window, use the lab value on the target day; if not available, use the lab value immediately after the target visit day.

A Wilcoxon rank sum test will be used to compare proportional change from baseline to Day 8, or Day of Discharge if prior to Day 8, between treatment groups. The between treatment group rank sum test is considered the primary analysis of the primary endpoint.

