7.4 Significance

All statistical tests and confidence intervals will use a 2-sided analysis with a significance level of $\alpha = 0.05$.

8 Safety Analysis

The following safety analyses will be based on the Safety population and on-treatment data scope. Additional safety analyses are detailed in [Section 11.4](#).

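### SAP 11.2 labels its Day 3, 5 and 8 estimates as per-dose effects, but they are cumulative from baseline, so the later ones cannot be credited to the latest dose

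*SAP*

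**What the plan says.** SAP 11.2 announces a separate set of analyses for each dosing instance, "such that the effect on D-dimer of each incremental dose of rNAP2 is estimated". It then models them on the primary analysis, matching it in "formulation to the Primary Efficacy Analysis as specified above, with estimates of instantaneous treatment effect at Days 3, 5, and 8". As to who is compared on each of those days, the section specifies that the estimates are "for subjects receiving 1, 2 or 3 doses of rNAPc2 or receiving SoC heparin through days 1, 3, and 7, respectively".

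The analysis referred to is in SAP 7.1.1: "A Wilcoxon rank sum test will be used to compare proportional change from baseline to Day 8" (or discharge, if earlier) between treatment groups. SAP 7.1 fixes the baseline at the Day 1 visit. SAP 7.4 makes all tests two-sided at 0.05.

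On duration of action, Protocol 2.2 reports: "The mean $t_{1/2}$ values ranged from 47.0 to 64.1 hours following the first dose on Day 1". Protocol 4.3 adds that steady state is not reached within the 8-day efficacy period and that exposure rises after each dose. Both rNAPc2 regimens plan doses on Days 1, 3 and 5 (Protocol 6.1.2).

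**The concern.** The two halves of the SAP 11.2 paragraph describe different quantities. The effect of an incremental dose is what that dose adds to those already given. A comparison of change from the Day 1 baseline measures everything since randomization. The two agree at Day 3, when one dose has been given. They part at Days 5 and 8 whenever an earlier dose worked and some of its effect remains.

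Nothing in the paragraph re-bases D-dimer to the value before the latest dose, conditions on the preceding value, or contrasts the Day 3, 5 and 8 effects with one another. With complete sampling on every day, the analysis would still answer the cumulative question.

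At stake is what the report may say about the second and third doses. If the labels carry over into tables, a Day 8 difference could be read as a benefit of the third dose that the analysis never isolated.

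**Working it through.** **1. What is estimated.** Percent change from baseline ranks participants exactly as the log ratio to baseline does, so work on the log scale. Let d1, d2 and d3 be the contributions of the three doses to the difference from heparin, f(t) the fraction of d1 still present on day t, and g(t) the same for d2.

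- Day 3: d1
- Day 5: f(5)·d1 + d2
- Day 8: f(8)·d1 + g(8)·d2 + d3

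An incremental estimate at Day 8 would target d3 alone. The planned one differs from it by f(8)·d1 + g(8)·d2.

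**2. Is carry-over plausible?** Drug left from dose 1 is 0.5^(hours/half-life), with half-lives of 47.0 and 64.1 h (Protocol 2.2):

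- 48 h: 49–60%
- 96 h: 24–35%
- 168 h: 8–16%

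This describes drug, not D-dimer effect. The documents give no duration for the latter.

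**3. The plan's own figures.** "approximately 160 participants will be enrolled and randomized 1:1:2 to rNAPc2 dose regimen 1, rNAPc2 dose regimen 2, and heparin SoC" (SAP 2.2). With 20% not evaluable, 160 × 0.8 = 128, or 64 pooled rNAPc2 against 64 heparin, which agrees with the stated approximate 130. The stated power for a 30% reduction at that size is 88.3%. It cannot be reproduced, because no SD is given and the table averages over conditions not listed. Under the approximation in step 4, the 160-participant row implies log SDs of 0.49, 0.55, 0.63, 0.72 and 0.80 for reductions of 20% to 40%. Such averaging means no single SD need fit, so this is not evidence of an error. No power figure is given for the per-dose analyses.

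**4. Size of the possible false credit at Day 8.** Inputs: 64 per arm; two-sided 0.05; dose 1 lowers D-dimer by 30%, so d1 = −ln(0.7) = 0.357; d2 = d3 = 0. Assumption: the log SD of change is 0.6 to 1.0. For the rank-sum test under normality, effective n = 64 × 3/π = 61.1, and

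z = f × 0.357 / (SD × √(2/61.1)) = f × 1.972 / SD

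rejection = Φ(z − 1.96) + Φ(−z − 1.96)

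| Fraction f left at Day 8 | SD 0.6 | SD 0.8 | SD 1.0 |
|---|---|---|---|
| 1 | z 3.29, 91% | z 2.46, 69% | z 1.97, 51% |
| 0.5 | z 1.64, 38% | z 1.23, 23% | z 0.99, 17% |
| 0.12 | z 0.39, 7% | z 0.30, 6% | z 0.24, 6% |

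Simulated rank-sum tests give about 47–90%, 16–39% and 5–6% for the three rows.

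**5. If the effect fades at the drug's half-life after Day 3** (SD 0.65, simulated), rejection is 32% (47.0 h) or 43% (64.1 h) at Day 5, and 7% or 13% at Day 8. On this path the distortion is greater at Day 5 than at Day 8.

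**6. Would re-basing to Day 3 repair it?** Assume half the variance of the Day 8 change arises before Day 3, so the Day 3 to Day 8 SD is SD/√2. With inert later doses the contrast shifts by (1 − f) × 0.357 towards a rise on rNAPc2, and z = (1 − f) × 1.972 × √2 / SD = (1 − f) × 2.789 / SD.

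- f = 1: 5%
- f = 0.5: 64% (SD 0.6) to 29% (SD 1.0); simulated 28–62%
- f = 0.12: 98% to 69%; simulated 68–99%

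Re-basing is clean only if the first effect is stable. Otherwise inert doses appear to raise D-dimer. In the other direction, later doses that merely hold an effect which would have faded would show no difference.

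**The case against.** The best defence is that SAP 11.2 sets no formal hypothesis for any one dose. It speaks of estimates, and it describes participants as having received one, two or three doses, which can be read as the effect after that many doses. That is fair: the 5% benchmark in the working belongs to a null the SAP does not state, and no table title is given that would attribute Day 8 to the third dose. But the same paragraph calls the doses incremental and the effect instantaneous, and it defines neither term. The reading that matches the specified analysis is not the one the labels convey.

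It may also be said that a Bayesian model does the work. That model is in the preceding paragraph, for subgroups; the per-dose set is described separately and tied to the primary analysis. SAP 14.2 shows only headings in the available text, so a model description that could not be read there cannot be excluded.

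Two stronger inferences are tempting. One is that the Day 8 analysis will nearly always credit an inert third dose. That needs full persistence of the D-dimer effect, and the cited half-life concerns drug level. The other is that the Phase 3 regimen would be chosen wrongly. No document ties the per-dose analysis to that choice; both Phase 2b regimens have three doses, and SAP 5.6 analyses each regimen separately.

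**Conclusion.** The point holds as a mismatch between the stated target and the specified analysis, and it should be corrected. The Day 5 and Day 8 estimates are cumulative and cannot support a statement about what the second or third dose adds.

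The mismatch follows from the text and needs no assumption. Its numerical consequence does: for a 30% first-dose effect, inert later doses, 64 per arm and log SD 0.6 to 1.0, Day 8 rejection runs from near 5% to about 90%, depending on a persistence the documents do not give. The upper end is a scenario, not a forecast.

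The primary Day 8 comparison of pooled rNAPc2 with heparin is unaffected, since the cumulative effect is what it is meant to test. A reader might infer that a different contrast would recover each dose's own effect. It would not: no arm is randomized to fewer planned doses, so randomization does not identify the increment.

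**What to change.** In SAP 11.2:

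1. Relabel the estimates as cumulative effects against heparin from baseline to Days 3, 5 and 8, after one, two and three doses.
2. Delete *incremental* and *instantaneous*.
3. State that the design does not identify the separate effect of dose 2 or dose 3, because no arm is randomized to fewer doses.

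This costs only wording and is right however long the first dose's effect lasts.

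A between-arm contrast from Day 3 to Day 8 or discharge is optional. If added, label it as net change over the interval, mixing any added effect with waning of the first dose, and not as the benefit of later doses. It uses central draws already in Protocol Table 2b, but with limits the SAP should state. The pre-dose requirement is written for the Day 1 sample only; the Day 3 visit has a window of ±1 day, so some Day 3 values may follow the second dose; and participants discharged by Day 3 contribute no interval.

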8 STUDY ASSESSMENTS AND PROCEDURES

8.1 STUDY PROCEDURES

8.1.1 SCHEDULE OF ACTIVITIES

Table 2a. Schedule of Activities (SoA)

Activity	Screen Day -7 to 1	Baseline Day 1	Day 2 (24h post-dose \pm 2h)	Day 3 \pm 1d	Day 5 \pm 1d	Day 8 \pm 1d	Day of Hospital Discharge	Day 30 \pm 3d
Informed consent	x							
Assess eligibility	x	x						
Randomize		x						
Medical history (COVID-19, cardiovascular, medical/ surgical history) ^b		x						
Concomitant medication ^b		x	x	x	x	x	x	x ^d
Baseline demographics ^b	x							
Focused physical examination, vital signs, weight, height ^b		x						
Study medication ^c		rNAPc2 7.5 μ g/kg SC on Day 1 and 5 μ g/kg SC on Days 3 and 5 or rNAPc2 5 μ g/kg SC on Day 1 and 3 μ g/kg SC on Days 3 and 5 or heparin per SoC						
Local laboratory values	x ^a	Record values of interest performed in the hospital clinical laboratory until hospital discharge or day 30 visit (whichever is first). In the case where a lab test is measured multiple times per day, the first scheduled values as well as any additional values that represent a clinically significant change should be reported.						
Assess need for inpatient medical services & complete ACTT			Daily until discharged to outpatient status or death or Day 30 reached					
Clinical & adverse events ^g	x	x	x	x	x	x	x	x ^d
Post-COVID functional status (PCFS) scale							x ^h	x ^d
Vital status								x ^d
Healthcare utilization							x	x ^d
Central Laboratory assessments (see Table 2b)		x	x	x ^e		x ^f	x ^f	x ^e

^a Local lab D-dimer drawn during hospitalization and prior to randomization will be used for eligibility and randomization stratification

^b May be obtained/extracted from medical record to minimize staff exposure to COVID-19

^c rNAPc2 must be dosed on Days 1, 3 and 5; only one rNAPc2 dose regimen is anticipated in Phase 3; Participants randomized to receive heparin will have doses administered per standard of care (SoC)

^d Participants who are discharged prior to Day 30 may have these activities performed remotely

^e For phase 2b only

^f If participant is discharged prior to Day 8, central laboratory assessments should be performed at hospital discharge

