8.1.2 LABORATORY SAMPLES AND VALUES

Participants will have laboratory samples collected and analyzed both locally and centrally in accordance with the SoA.

Local Laboratory Values

Laboratory tests of interest listed below, obtained via the local laboratory that are used to assess eligibility*, or are collected during the participant's enrollment until hospital discharge or Day 30 visit (whichever is first) should be reported via the eCRF. In the case of D-dimer, initial value (eligibility) is preferred as collected at the time of hospital admission, prior to initiation of heparin treatment. In the case where a lab test is measured multiple times per day, the first scheduled values as well as any additional values that represent a clinically significant change should be reported.

- Hemoglobin
- D-dimer*
- White blood cell count (WBC)
- Platelet count*
- Estimated glomerular filtration rate (eGFR)*
- Aspartate aminotransferase (AST)
- Alanine aminotransferase (ALT)
- Total bilirubin
- Prothrombin time (PT)
- Partial thromboplastin time (PTT)
- Troponin
- Brain natriuretic peptide (BNP)

Central Laboratory Sample(s)

Central laboratory samples should be collected and shipped to the central laboratory as described in the Laboratory Manual. The following table outlines the samples that will be collected and analyzed via the central laboratory.

Table 2b. Central Laboratory Blood Collection

Day 1 ^a	Day 2 (24h post-dose)	Day 3 Phase 2b only	Day 8 ^b , or Day of Hospital Discharge (if prior to Day 8)	Day 30 Phase 2b only
Samples for clinical laboratory tests				
IL-6, hsCRP			IL-6, hsCRP	
D-dimer, PT, PTT, factor Xa tissue factor, antiphospholipid antibody	D-dimer, PT, PTT	D-dimer, PT, PTT	D-dimer, PT, PTT, factor Xa tissue factor, antiphospholipid antibody	antiphospholipid antibody
ADA for rNAPc2 subjects (Phase 2b only)	PK sample for rNAPc2 subjects (Phase 2b only)		PK sample for rNAPc2 subjects (Phase 2b only)	ADA for rNAPc2 subjects
Samples for future research use^c				
Future use serum and plasma aliquots and buffy coat			Future use serum and plasma aliquots	

^a Baseline Central Laboratory sample should be collected before administration of study medication (rNAPc2 or heparin). A sample up to 1-hour post-administration is acceptable.

^b For rNAPc2-allocated participants, Day 8 Central Laboratory samples should be collected before that day's dose of SoC thromboprophylaxis, if prescribed.

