2.5 Secondary Endpoints

2.5.1 Efficacy

Secondary efficacy endpoints are:

- Change in D-dimer level from baseline to 24 hrs post the institution of study medication following randomization (Study Day 2), and 48 hours after institution of study medication (Study Day 3)
- Probability of discharge as assessed by ACTT ≥ 6 by Day 8 and Day 30 post randomization
- Composite of death, thrombosis, organ support, or rehospitalization within 30 days adjudicated as to its relatedness to COVID-19
- Change in biomarkers associated with outcomes including those related to coagulation and inflammation from baseline through Day 8

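### SAP 11.2 plans a two-dose D-dimer effect at Day 5 that no scheduled sample supports, and its one-dose effect at Day 3 lacks a stated draw order relative to the second dose

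*SAP*

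**What the plan says.** SAP 11.2 describes a separate set of analyses for each dosing instance, "such that the effect on D-dimer of each incremental dose of rNAP2 is estimated". It ties them to the primary analysis in these words: "formulation to the Primary Efficacy Analysis as specified above, with estimates of instantaneous treatment effect at Days 3, 5, and 8 for subjects receiving 1," with two and three doses following in turn. Heparin comparators are defined by how long they had received heparin. The Schedule of Activities (Protocol 8.1.1, footnote c) says "rNAPc2 must be dosed on Days 1, 3 and 5", so the second and third doses fall due on the same nominal days as the Day 3 and Day 5 estimates.

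The sampling is set elsewhere. In the Schedule of Activities, the row "Central Laboratory assessments (see Table 2b") is marked for baseline, Day 2, Day 3, Day 8, discharge and Day 30. Its Day 5 cell is empty. Table 2b (Protocol 8.1.2) lists "D-dimer, PT, PTT, factor Xa tissue factor, antiphospholipid antibody" for Day 1 and again for Day 8 or earlier discharge, and D-dimer with PT and PTT on Days 2 and 3. It has no Day 5 column. The Day 5 visit in Protocol 8.1.3 lists local results only, where the hospital has them. Footnote f adds: "If participant is discharged prior to Day 8, central laboratory assessments should be performed at hospital discharge".

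For Day 3, SAP 2.5.1 gives the time as "48 hours after institution of study medication (Study Day 3"), and Protocol 8.1.3 allows one day either side. The Day 3 visit includes both a dose and a central sample, and neither document says which comes first.

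**The concern.** An estimate of the effect of two doses at Day 5 needs a Day 5 D-dimer in all arms, taken before the third dose. An estimate of the effect of one dose at Day 3 needs a sample taken before the second. The schedule does not supply the first and does not secure the second.

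Phase 2b is meant to identify a regimen and to inform the Phase 3 dose. A pre-specified result described as the effect of each further dose could be given weight in that discussion. If its middle estimate comes from participants whom unblinded clinicians chose to test, or who were well enough to go home, a difference between arms could reflect who was sampled and not what was given. If some one-dose samples in fact follow dose 2, the step from one dose to two is blurred as well.

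**Working it through.** There is no stated figure to reproduce for this analysis. The check sets the SAP's three estimates against the sampling schedule.

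| SAP 11.2 estimate | Visit window (Protocol 8.1) | rNAPc2 dose due at that visit | Scheduled central D-dimer | Order of draw and dose |
|---|---|---|---|---|
| 1 dose, Day 3 | Days 2 to 4 | second | yes, all Phase 2b participants | not stated |
| 2 doses, Day 5 | Days 4 to 6 | third | none | not applicable |
| 3 doses, Day 8 | Days 7 to 9 | none | yes, or at earlier discharge | not an issue for study drug |

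**Count.** Table 2b has five collection columns. Four include D-dimer (Days 1, 2, 3, and 8 or discharge); Day 30 does not. Draws on Day 5 for a participant still in hospital: 0 of 4. Estimates without scheduled data: 1 of 3.

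**What could fill Day 5.** There are two sources.
- Local D-dimer, recorded when the hospital happens to run it. SAP 2.3 says the investigators and treating team know the assignment, so the decision to test can depend on arm and on clinical course.
- Central discharge samples from those leaving around Day 5. Exclusion criterion 6 (Protocol 5.2) removes patients expected to leave within 5 days, so these should be few and unusually well.

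**Do the primary-analysis rules help?** The window of 48 h either side in SAP 7.1.1 is written only for Day 8 or discharge. If it were carried over (the SAP does not say), Day 5 ± 2 gives Days 3 to 7. That takes in the scheduled Day 3 sample, possibly before dose 2, and samples after dose 3. The visit windows themselves overlap: Days 2 to 4 and Days 4 to 6 share Day 4.

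**Day 3.** With the first dose on Day 1, a window of Days 2 to 4 means samples roughly 24 to 72 h after that dose, against the nominal 48 h at which the second is due. Both orders are allowed. Protocol 6.4 asks for dates of administration and does not mention clock times, so same-day order may not be recoverable afterwards.

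**Precision at Day 5, by assumption only.** The documents give no share of participants with a Day 5 local value, so I take a share f of 160, split equally: n per arm = 160f/2. For a 30% reduction, the log-scale effect is −ln(0.70) = 0.357. Back-solving the SD from the plan's 88.3% power at 128 evaluable (64 per arm): 0.357 / [(1.960 + 1.190) × √(2/64)] = 0.64. Then power = Φ(0.357 / (0.64 × √(2/n)) − 1.96).

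| f | n per arm | Power |
|---|---|---|
| 20% | 16 | 35% |
| 40% | 32 | 61% |
| 60% | 48 | 78% |
| 80% | 64 | 88% |

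The last row matches the plan by construction. The five cells of that row of the power table imply SDs from 0.50 to 0.82. At f = 40%, √(2/32) = 0.25, so power runs from Φ(0.357/0.205 − 1.96) = 41% to Φ(0.357/0.125 − 1.96) = 81%. These figures show loss of precision only. The selection problem would remain at any f.

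**The case against.** The strongest reply is that this is one supportive paragraph, that Day 5 data are not wholly absent, and that much of the Day 3 complaint is inference. Several parts of that stand.

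- SAP 2.5.1 does tie Day 3 to the first dose, and the sample is scheduled for everyone in Phase 2b. The Day 3 difficulty is possible mistiming, not selection.
- SAP 11.2 never says that a sample taken after dose 2 would count as one-dose. Its reference to participants receiving one dose can be read as excluding such samples. The rule is unstated, not wrong.
- The order of bullets in the visit lists proves nothing. The baseline list places the 24-hour sample ahead of randomization. The Day 8 timing footnote concerns standard-of-care thromboprophylaxis, so only Day 1 has an instruction relative to study drug.
- Collection details are deferred to a Laboratory Manual that is not among the documents. It might fix the Day 3 order. It is unlikely to supply a Day 5 D-dimer that neither Table 2a nor Table 2b contains.
- Local values are recorded, SAP 7.1.1 accepts local pairs, and laboratory source is a listed subgroup. Some Day 5 values may exist. That supports an exploratory label, not an estimate on a par with Day 8.

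A reader might go further and infer that the Day 3 secondary endpoint is compromised. The documents do not support this: that endpoint compares randomized groups at a time point and makes no one-dose claim. A reader might also infer that Phase 2b would use this analysis to settle how many doses to give. Both regimens have doses on Days 1, 3 and 5, no section assigns the analysis that role, and SAP 5.6 assesses the regimens by analysing each dose group separately.

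**Conclusion.** The point holds in two limited parts. First, the two-dose estimate at Day 5 has no scheduled sample behind it (0 of 4 central D-dimer draws; 1 of 3 planned estimates). It would rest on a subset selected after randomization, in groups defined by treatment received. This follows directly from the two documents. Second, the one-dose estimate at Day 3 may mix samples from before and after dose 2, because no order is stated. This rests on reading one dose at Day 3 as meaning before the second dose, and on the Laboratory Manual not already fixing the order. The documents give no share of samples affected in either case, so the size of any bias cannot be computed.

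The Day 8 primary comparison is untouched, and the randomized Day 3 comparison is not invalidated. The change is worth making because the analysis is pre-specified, claims more than the schedule can deliver, and is cheap to correct.

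**What to change.** 1. **Day 3 draw.** In Table 2b and the Day 3 visit, state that the Day 3 central sample is drawn before that day's rNAPc2 administration, and record draw and dose times. In SAP 11.2, count as one-dose only samples drawn before the second dose, and report how many are set aside. The collection instruction matters more than the analysis rule, since excluding samples afterwards creates a smaller selected subset of its own.
2. **Day 5 estimate.** In SAP 11.2, drop it together with the claim to estimate the effect of each further dose. Otherwise label it exploratory in a selected subset, and name its source (local or discharge sample), its window, and the number contributing per arm.
3. **What to rely on instead.** Use the D-dimer time course at Days 2, 3, and 8 or discharge, for each randomized regimen against heparin. Most of this is already planned through the secondary endpoints and the regimen subgroup.

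The cost is a table footnote, time fields for draw and dose if these are not already collected, and a few lines of SAP text. The sponsor loses or downgrades a Day 5 estimate that the schedule does not support.
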